### 8.4.5 **Primary Efficacy Endpoint**

### 8.4.5.1 Primary Efficacy Hypothesis

The primary efficacy endpoint for this study is the proportion of CAT responders, defined as an improvement from baseline  $\geq 2$ , at Week 12. This will be evaluated for the null hypothesis that the proportion is not different than 0:

H0: 
$$p = 0$$
 vs. H1:  $p > 0$ 

Where p is the proportion of subjects at Week 12 with an improvement from baseline of at least 2 in CAT total score. A two-sided unadjusted 95% confidence interval for the proportion will be used to determine study success with the lower bound of the CI > 0 indicating success.

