## 9.1 Statistical Hypotheses

The aim of this study is to quantify both improvement CAT scores and responder proportions in subjects with moderate/severe COPD treated with ensifentrine (3 mg) for 12-weeks. No formal statistical tests will be performed. Study conclusions will be based on two-sided unadjusted 95% confidence intervals for estimated change and derived proportions.

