## 9.2 Sample Size Determination

A sample size of approximately 20 subjects provides the ability to demonstrate a responder proportion estimate statistically differs from zero. Assuming a 30 percent response rate in the study population, 20 subjects provides the ability to demonstrate the derived proportion differs from zero determined by the lower two-sided 95% confidence limit derived from the estimated count using a normal approximation assuming a standard error equal to the square root of 6.

Twenty subjects also provides the ability to demonstrate the estimates of mean change from baseline does not extend to the clinically meaningful deterioration limit of (+2 units). Assuming estimated mean improvement of 1 unit with a corresponding standard deviation equal to 4.5, 20 subjects provides the ability to demonstrate the upper 95% confidence interval for a mean change from baseline estimate does not exceed 2 units.

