# 5 Sample Size Justification

A sample size of approximately 20 subjects provides the ability to demonstrate a responder proportion estimate statistically differs from zero. Assuming a 30 percent response rate in the study population, 20 subjects would provide an expected count of 6 events. The two-sided 95% confidence interval for the number of events generated via normal approximation is (1.199, 10.801). Thus,20 subjects provide the ability to demonstrate the derived proportion differs from zero determined by the lower two-sided 95% confidence limit derived from the estimated count using a normal approximation assuming a standard error equal to the square root of 6.

Twenty subjects also provide the ability to demonstrate the estimates of mean change from baseline does not extend to the clinically meaningful deterioration limit of (+2 units). Assuming estimated mean improvement of 1 unit with a corresponding standard deviation equal to 4.5, 20 subjects provide the ability to demonstrate the upper 95% confidence interval for a mean change from baseline estimate does not exceed 2 units.

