### 8.4.5.2 Primary Efficacy Analysis

The FAS population will be used to assess the primary efficacy endpoint of proportion of CAT total score responders defined as improvement from baseline  $\geq 2$  at Week 12. The proportion of subjects classified as responders at week 12, standard errors, and corresponding 95% CI will be estimated by negative binomial regression with timepoint and background therapy (LABA+LAMA or LABA+LAMA+ICS) included as fixed effects, and with baseline CAT total score included as a covariate. The scale parameter in the negative binomial model will be held fixed by specifying a noscale option.

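### SAP 8.4.5.1 adds a test of p = 0 and a success label that the protocol does not call for, and that label says little about a drug effect

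*SAP*

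**What the plan says.** Protocol 9.1 is descriptive: "No formal statistical tests will be performed. Study conclusions will be based on two-sided unadjusted 95% confidence intervals". It states no null hypothesis and no success criterion. Zero does appear in protocol 9.2, but as the benchmark for sizing: "20 subjects provides the ability to demonstrate the derived proportion differs from zero determined by the lower two-sided 95% confidence limit".

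SAP 8.4.5.1 goes further. It writes down H0: p = 0 and H1: p > 0, where p is the proportion of subjects whose CAT total score improves by at least 2 at Week 12, and says that the two-sided 95% interval "will be used to determine study success with the lower bound of the CI > 0 indicating success". SAP 2.2 records no change to the planned analyses.

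The interval is to come from the model in SAP 8.4.5.2: "standard errors, and corresponding 95% CI will be estimated by negative binomial regression with timepoint and background therapy", with baseline CAT as covariate. On dispersion that section says: "The scale parameter in the negative binomial model will be held fixed by specifying a noscale option". It gives neither the value at which the parameter is fixed nor the scale on which the interval is formed.

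**The concern.** All subjects receive ensifentrine, and neither document gives a responder rate for untreated or placebo subjects. The value p = 0 means that nobody improves by 2 points on a 0-40 questionnaire. CAT scores vary from visit to visit, so some subjects will cross that line even if the average does not move. Rejecting p = 0 therefore shows only that some subjects score at least 2 points better. It does not show that the drug caused this.

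What is at stake is how the primary result is read. A report stating that the study met its success criterion invites the reader to take it as evidence of efficacy, which an uncontrolled proportion compared with zero cannot supply.

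**Working it through.** **Inputs from the documents.** n = 20, a 30% response rate, and a standard error of √6 for the count (protocol 9.2, SAP 5). For the companion calculation on the mean: "Assuming estimated mean improvement of 1 unit with a corresponding standard deviation equal to 4.5". A responder improves by ≥ 2 (SAP 8.4.5.1). The CAT total is an integer, the sum of 8 items scored 0-5 (SAP 8.4.6.2).

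**Assumptions not in the documents.** Change is normal, and SD 4.5 also holds at zero mean change. Ranges below run from a continuous score to an integer score (cut at -1.5).

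**1. The plan's own figure.** 20 × 0.30 = 6, and 6 ± 1.96 × √6 = (1.199, 10.801). This matches SAP 5. Divided by 20 it is 6.0% to 54.0%.

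**2. Responders at zero mean change.**

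| SD | Continuous, Φ(-2/SD) | Integer, Φ(-1.5/SD) |
|---|---|---|
| 3 | 25% | 31% |
| 4.5 | 33% | 37% |
| 6 | 37% | 40% |

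At SD 4.5 both values exceed the 30% planning rate. At SD 3 they lie on either side of it. The other planning assumption (mean improvement 1, SD 4.5) implies Φ(-1/4.5) = 41% to Φ(-0.5/4.5) = 46% responders, so under normality the two planning assumptions do not agree with each other.

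**3. How often success would be declared at zero mean change, SD 4.5.** The answer depends on how the limit is formed.

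- *Count ± 1.96√count.* The lower limit is 3 - 1.96√3 = -0.39 for 3 responders and 4 - 1.96√4 = +0.08 for 4, so 4 are needed. P(X ≥ 4) with n = 20 is 93.4% (p = 0.328) to 97.0% (p = 0.369). With 18 analysed it is 89-94%. At SD 3 and n = 20 it is 78-91%.
- *Standard error fixed at √6, as in SAP 5.* 4 - 1.96√6 = -0.80 and 5 - 1.96√6 = +0.20, so 5 are needed: 84-91% (n = 20), 76-85% (n = 18).
- *Log scale.* The limit is exp(estimate - 1.96 × SE), which is always above 0. The rule cannot fail if the model converges.
- *SAP 8.4.5.2 model with a delta-method limit.* The lower limit is m(1 - 1.96 × SE), with SE on the log scale. It is above 0 only if SE < 1/1.96 = 0.51. Simulated results:

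| Analysed; triple/dual split | Dispersion 0 | Dispersion 1 |
|---|---|---|
| 20; 10/10 | 84-92% | 70-82% |
| 20; 5/15, equal weights | 70-82% | 48-62% |
| 18; 9/9 | 77-86% | 56-69% |
| 18; 5/13, equal weights | 65-76% | 39-53% |

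The simulation used Week 6 and Week 12 rows, a log link, model-based standard errors, 12,000 runs per cell, within-subject correlation 0.6, and baseline N(20, 6) clipped to 10-40 and independent of change. These settings are assumptions. With correlation 0.3, the 10/10 split at dispersion 0 gives 86-93%, which is the top of the 40-93% range; the last row of the table is the bottom. In 0.1-7% of runs the model did not converge, and these were counted as not successful.

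For comparison, at the planned mean improvement of 1 with n = 20, the 10/10 split gives 96-98% (dispersion 0) and 90-95% (dispersion 1), and the 5/15 split gives 88-93% and 73-83%.

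**4. Which precision interval belongs in SAP 5.** For 6 of 20 in an intercept-only negative binomial model with dispersion k, SE(log) = √((1/0.3 + k)/20). With k = 0 this is 0.408, and the delta interval is 0.3(1 ± 1.96 × 0.408) = 6.0-54.0%, the same as the interval SAP 5 prints. With k = 1 it is 0.465, giving 2.6-57.4% (delta) or 12.0-74.7% (log). The exact binomial interval, 11.9-54.3%, matches none of these.

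**The case against.** The strongest reply is that little depends on the label. No interim look, testing hierarchy or later decision is tied to it. The population, model, estimate and interval are the same with or without it. The zero benchmark comes from protocol 9.2, which sizes the study on the lower 95% limit, so the SAP adds only the hypothesis pair and the word success. The 33-37% is not a figure from the documents either: it moves an SD that was paired with a mean improvement of 1 to a mean of zero, and it adds normality. All of this stands, and it limits the point to the label.

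It does not remove the point. Protocol 9.2 uses zero to justify a sample size, whereas SAP 8.4.5.1 turns it into a verdict on the study, after protocol 9.1 has excluded formal tests. The result is also not sensitive to the SD: over 3 to 6, between 25% and 40% respond at zero mean change.

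Three stronger readings are tempting, and the documents support none of them:

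- A reader might infer an inflated type I error. If some subjects truly improve by 2 points, rejecting p = 0 is correct; the null is uninformative.
- A reader might infer that the rule always passes. That is so only on the log scale and only when the model converges. With a delta-method limit it can fail often.
- A reader might infer that the primary analysis is invalid. The objective is to assess a proportion, and that proportion is still reported with its interval.

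**Conclusion.** The point holds, limited to the hypothesis pair and the success label in SAP 8.4.5.1. They conflict with protocol 9.1, and meeting the criterion would say little about a drug effect. Under normal change with SD 4.5, 33-37% of subjects respond at zero mean change. Success is then declared in 93-97% of trials under count ± 1.96√count with n = 20, in roughly 40-93% under the covariate model with a delta-method limit, and whenever the model converges on the log scale. The spread arises because SAP 8.4.5.2 leaves the interval scale and the fixed dispersion value open, and because the background split and weighting are not known. None of these figures is a floor. The issue should be fixed, but it does not change what is estimated.

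**What to change.** In a SAP version dated before database lock:

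1. **SAP 8.4.5.1:** delete H0/H1 and the success sentence. Report the Week 12 responder proportion with its 95% CI as descriptive, in line with protocol 9.1.
2. **SAP 8.4.5.2:** state the scale of the interval and the fixed dispersion value.
3. **SAP 5:** replace the claim of showing a difference from zero with a statement of expected precision. Use the interval already printed (1.199 to 10.801 of 20, or 6.0-54.0%), or one computed from the SAP 8.4.5.2 model once item 2 is settled. An exact binomial interval should not be used, because the planned analysis will not produce one.
4. **Protocol 9.2:** align the wording at the next amendment. Until then it will differ from SAP 5 in wording.

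The general significance convention in SAP 8.1 and the Type 3 effects table (14.2.1.2) are peripheral and need not change for this purpose.

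The cost is SAP text. No subjects, visits or data are affected, and items 1 to 3 need no protocol amendment. The downside is that the study will report no pass/fail result.

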### 8.4.5.2 Primary Efficacy Analysis

The FAS population will be used to assess the primary efficacy endpoint of proportion of CAT total score responders defined as improvement from baseline  $\geq 2$  at Week 12. The proportion of subjects classified as responders at week 12, standard errors, and corresponding 95% CI will be estimated by negative binomial regression with timepoint and background therapy (LABA+LAMA or LABA+LAMA+ICS) included as fixed effects, and with baseline CAT total score included as a covariate. The scale parameter in the negative binomial model will be held fixed by specifying a noscale option.

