## 9.3.2 Statistical Analyses

Continuous endpoints will be summarized as change from baseline using a mixed model for repeated measures with model terms for time and background therapy, and with baseline included as a covariate. Within subject error will be modeled using an unstructured covariance matrix, and Kenward-Roger method will be used to estimate degrees of freedom. Least square mean estimates, standard errors, and corresponding 95% confidence limits will be presented at each post-treatment time of assessment.

Response frequencies will be summarized by negative binomial regression with model terms for time and background therapy, and with baseline included as a covariate. Within subject correlation in responder status will be modeled using an unstructured covariance matrix. Response proportions, standard errors, and corresponding 95% confidence limits will be generated from estimated frequencies and presented for each post-treatment time of assessment.

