## 9.3.3 Efficacy Analyses

Analysis will be based on the FAS.

Continuous variables will be summarized both for the absolute value and for change from baseline using descriptive statistics (N, mean, median, SD, minimum, and maximum), generated separately as well as overall.

Results will provide the number of subjects included in each analysis, estimated least square means and corresponding standard errors and 95% confidence intervals (CIs).

Total score data will be used for the change from baseline CAT analysis and the responder analysis.

Individual CAT item score (8-items) will be used for the change from baseline item-level analysis.

An analysis of the proportion of subjects with an improvement from baseline in CAT score of 2 or more will be summarized by visit and analyzed using negative binomial regression.

CAT total score and the individual item scores will be listed for each visit (items: Cough, Mucus, Chest Tight, Breathless, Limited Activities, Confident, Sleep and Energy). A plot of the least square means change from baseline in total score over time will be presented (based on the MMRM analysis).

Additional details will be provided in the SAP.

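### The primary estimate comes from a covariate-adjusted regression whose output is not, in general, the Week 12 responder proportion the SAP defines, and no passage says how one becomes the other

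*SAP*

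**What the plan says.** SAP 8.4.5.1 fixes the target: "Where p is the proportion of subjects at Week 12 with an improvement from baseline of at least 2 in CAT total score". That is a count over a number of subjects, with no conditioning on anything.

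SAP 8.4.5.2 gives the estimator: "The proportion of subjects classified as responders at week 12, standard errors, and corresponding 95% CI will be estimated by negative binomial regression". Timepoint and background therapy (dual or triple) are fixed effects, "with baseline CAT total score included as a covariate". On dispersion it adds: "The scale parameter in the negative binomial model will be held fixed by specifying a noscale option". It does not give the value at which the parameter is held.

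On turning model output into a proportion, Protocol 9.3.2 says: "Response proportions, standard errors, and corresponding 95% confidence limits will be generated from estimated frequencies". Protocol 9.3.3 adds, for efficacy results in general: "Results will provide the number of subjects included in each analysis, estimated least square means and corresponding standard errors". Neither document names the link function, the baseline CAT value at which the proportion is evaluated, the weights given to dual and triple therapy, or whether predictions are averaged over subjects. SAP section 11 places the output shells in a separate document.

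**The concern.** This is a single-arm study whose stated aim (Protocol 9.1) is to quantify change in CAT and responder proportions, so the Week 12 proportion is its main product. With one arm there is no treatment contrast for covariates to sharpen. They can only move the estimate away from the simple count.

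On the usual reading of a negative binomial model, the reported figure is the exponential of a linear predictor averaged on the log scale. That is a geometric-type mean of the group rates, taken at average baseline CAT, with the two background groups weighted equally whatever the enrolled mix. It is not responders/N. Two analysts following the same text could report different primary results from the same data, and the headline figure could disagree with the count and percentage printed beside it.

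**Working it through.** **Inputs from the documents.** About 20 subjects and a 30% response rate, so 6 expected responders (SAP 5). At most 10 subjects on triple therapy (Protocol 5.1, criterion 9). Model terms from SAP 8.4.5.2.

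**Assumed, because not stated.** Log link; least-squares mean at mean baseline CAT with 50:50 background weights; dispersion fixed at 0 or 1 (both tried); dual/triple splits of 10/10, 13/7 and 15/5.

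**The plan's own figure.** 6 ± 1.96 × √6 = 1.199 to 10.801 events, as SAP 5 states. Divided by 20, this is 6.0% to 54.0%. The planning calculation therefore treats the estimate as a count over 20, which is the definition in SAP 8.4.5.1 and not the model output of 8.4.5.2.

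**Background therapy alone.** Take the same response pattern at both visits and no baseline effect. The model then reproduces the two group rates, and the least-squares mean is √(p_dual × p_triple). Each row has 6 of 20 responders, an observed 30%. The result is the same at dispersion 0 and 1.

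| Dual | Triple | Calculation | Result | Gap (points) |
|---|---|---|---|---|
| 3/10 | 3/10 | √(0.3 × 0.3) | 30.0% | 0.0 |
| 4/10 | 2/10 | √(0.4 × 0.2) | 28.3% | -1.7 |
| 5/10 | 1/10 | √(0.5 × 0.1) | 22.4% | -7.6 |
| 5/13 | 1/7 | √(5/13 × 1/7) | 23.4% | -6.6 |
| 3/13 | 3/7 | √(3/13 × 3/7) | 31.4% | +1.4 |
| 3/15 | 3/5 | √(0.2 × 0.6) | 34.6% | +4.6 |

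The geometric mean of two rates cannot exceed their 50:50 arithmetic mean. With equal groups that arithmetic mean is responders/N, so the figure can only fall or tie. With unequal groups responders/N is weighted by enrolment, and the gap can take either sign.

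The choice of weights also matters. For 5/13 and 1/7, log-scale weights in the enrolled 13:7 ratio give exp(0.65 × ln 0.385 + 0.35 × ln 0.143) = 27.2%. The text therefore allows 30.0%, 27.2% or 23.4% from one data set.

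**Baseline CAT alone.** For a roughly normal covariate with log-scale slope b, the least-squares mean is the overall mean × exp(-(b·SD)²/2). At 30% the shortfall is 30 × (1 - exp(-(b·SD)²/2)): 0.15 points at b·SD = 0.1, 1.3 at 0.3, 3.5 at 0.5 and 6.5 at 0.7.

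**All terms together.** The simulations used 20 subjects, two visits and the SAP's model terms, with 600 trials per setting. Assumed Week 12 rates were 30, 50 and 60%, odds ratios 1 to 3 per SD of baseline and 0.33 to 3 for background, and 5 or 10 subjects on triple therapy. The gap is the least-squares mean minus the observed proportion:

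- 10/10 split: mean gap -1.4 to -8.1 points; above the observed value in 0 to 6% of trials.
- 15/5 split: mean gap -11.5 to +1.7 points; above the observed value in 4 to 71% of trials.
- No true covariate effect, 30% rate: mean gap -2.0 to -2.7 points. In 51 to 58% of trials the result was less than 2 points below the observed value, or above it.

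**Averaging instead.** Averaging predicted Week 12 values over subjects reproduced the observed proportion exactly at dispersion 0. At dispersion 1 the mean gap was 0.04 to 0.8 points.

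**Failure.** If a background group has no responder at either visit, its log rate has no finite estimate. With 5 subjects on triple therapy and a 30% rate, the chance is 0.7^10 = 2.8% if the visits are independent and 0.7^5 = 16.8% if they agree perfectly. SAP 8.4.6.1 has a non-convergence plan for the continuous endpoint; SAP 8.4.5.2 has none.

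**The case against.** The strongest reply is that SAP 8.4.5.2 never mentions a least-squares mean. The SAP uses that term only for change from baseline, and Protocol 9.3.2 likewise promises least-squares means for continuous endpoints while deriving responder proportions from estimated frequencies. That phrase is compatible with averaged predictions, and the separate output shells may settle the matter. This stands: the least-squares-mean reading is an inference from the general sentence in Protocol 9.3.3 and from usual practice. It does not close the gap, because neither the SAP nor the protocol states the step.

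A reader might also infer that the reported figure always sits below responders/N, by something like 2 to 10 points. The documents do not support that. The size depends on the baseline effect, the background effect and the dual/triple split, none of which is given, and 3/15 with 3/5 moves the estimate upwards.

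Two further points stand in part. The observed percentage will appear anyway, since Protocol 9.3 requires counts and percentages and 9.3.3 has the proportion summarised by visit; but the model figure is the one labelled primary. And a gap of 1 to 2 points is small beside a planning interval of 6% to 54%. Larger gaps need stronger covariate effects or an uneven responder split, both of which can occur with 20 subjects.

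**Conclusion.** The point holds as a mismatch between definition and estimator. SAP 8.4.5.1 defines a marginal proportion; SAP 8.4.5.2 estimates it from a covariate-adjusted model without saying how that proportion is recovered. If a log-link least-squares mean with equal background weights is used, it will generally differ from responders/N: nearly always lower with equal groups, in either direction with unequal ones. The mean gap was about -11 to +2 points across the assumed scenarios. Those figures rest on the assumed link, weights and covariate effects, so they illustrate the possible size and do not predict it.

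A reader might go further and conclude that the trial's success call is at risk. That is not shown. The criterion is a lower confidence bound above zero, and nothing here demonstrates that the choice of point estimate would reverse it. What is affected is the headline number, which is the main thing a single-arm estimation study reports.

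**What to change.** In SAP 8.4.5.2, make the primary estimate the observed number of Week 12 responders divided by the number of FAS subjects with a Week 12 CAT, with a binomial interval (exact or Wilson) from the same count. For 6 of 20 the exact 95% interval is 11.9% to 54.3%. This estimate needs no link, weights or covariate values, and it can be computed even when a background group has no responders.

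If the regression is kept as a supporting analysis, state the link and the dispersion value, obtain the proportion by averaging predicted Week 12 probabilities over FAS subjects instead of from a least-squares mean, and say what happens if the model cannot be fitted.

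The cost is a few lines of SAP text and minor programming, with no new data or subjects. The drawback is that it departs from the regression named in Protocol 9.3.2 and 9.3.3, so it must be recorded in SAP 2.2, which now says not applicable, as a change to the planned analysis.

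### The yes/no Week 12 primary endpoint is analysed with a count model, so its standard error and 95% CI are too wide; the sample-size standard error of √6 repeats the error

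*SAP*

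**What the plan says.** SAP 8.4.5.1 defines p as the proportion of subjects whose CAT total score has improved by at least 2 at Week 12. It adds: "A two-sided unadjusted 95% confidence interval for the proportion will be used to determine study success"; success means a lower limit above 0. Protocol 9.1 gives the interval the same role: "Study conclusions will be based on two-sided unadjusted 95% confidence intervals for estimated change and derived proportions".

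SAP 8.4.5.2 states that the proportion, standard error and CI "will be estimated by negative binomial regression with timepoint and background therapy (LABA+LAMA or LABA+LAMA+ICS) included as fixed effects", with baseline CAT as a covariate, and continues: "The scale parameter in the negative binomial model will be held fixed by specifying a noscale option". The method is not peculiar to the SAP. Protocol 9.3.3 says the responder proportion "will be summarized by visit and analyzed using negative binomial regression", and Protocol 1.1 and 9.3.2 name the same model. SAP 8.4.5.3 applies it to Week 6 as well, and adds a version with a subject-level robust standard error as a sensitivity analysis only.

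For sample size, Protocol 9.2 assumes 30% responders among 20 subjects and derives the lower limit "using a normal approximation assuming a standard error equal to the square root of 6". SAP 5 gives the resulting 95% interval as 1.199 to 10.801 events.

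**The concern.** A subject counts as 0 or 1 and cannot be a responder twice at Week 12, so the variance per subject is p(1−p). A negative binomial model assumes p + kp², with k the dispersion. This is larger for every k ≥ 0 and p > 0, so its model-based interval cannot have the right width for this endpoint. Holding the scale fixed is not the cause: even if k were estimated, the smallest value, k = 0, leaves the Poisson variance p, which is still too large.

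At stake is the headline result. In a single-arm study of about 20 subjects, showing that a responder rate exceeds zero is a very low bar. The informative output is the estimate and its interval, and that interval would not be a 95% interval.

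**Working it through.** **Inputs.** From the plan: n = 20, p = 0.30, expected count 6, two-sided 95% (z = 1.96). The plan states neither the fixed dispersion nor the link, so I assume k from 0 to 1 and show log and identity scales.

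**1. The plan's own figure.** 6 ± 1.96 × √6 = 6 ± 1.96 × 2.449 = (1.199, 10.801), or 6.0% to 54.0%. It reproduces exactly and is a Poisson interval.

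**2. The binomial counterpart.** √(20 × 0.3 × 0.7) = √4.2 = 2.049, giving 6 ± 1.96 × 2.049 = (1.98, 10.02), or 9.9% to 50.1%. The planned standard error is 2.449/2.049 = 1.195 times the binomial one. This step needs no assumption about k or link.

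**3. Inflation in the primary model (no covariates).** The standard error ratio is √((1 + kp)/(1 − p)). The binomial sample size with the same precision is 20(1 − p)/(1 + kp).

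| Responder rate | SE ratio, k = 0 to 1 | Equivalent n, k = 0 to 1 |
|---|---|---|
| 30% | 1.20 to 1.36 | 14.0 to 10.8 |
| 41–46% | 1.30 to 1.64 | 11.8 to 7.5 |
| 60% | 1.58 to 2.00 | 8.0 to 5.0 |

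The middle row is the rate implied by the plan's mean-change assumption (improvement 1, SD 4.5) if changes are normal: Φ((−2 + 1)/4.5) = 0.412, or Φ((−1.5 + 1)/4.5) = 0.456 allowing for integer scores. The 60% row is illustrative.

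**4. Intervals at 6/20.** Log scale: p × exp(±1.96 √((1/p + k)/20)), with −1 in place of k for the binomial. Identity scale: (x ± 1.96 √(x(1 + kp)))/20.

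| Method | 95% CI |
|---|---|
| Log scale, k = 0 | 13.5–66.8% |
| Log scale, k = 1 | 12.0–74.7% |
| Log scale, binomial | 15.4–58.6% |
| Identity scale, k = 0 | 6.0–54.0% |
| Identity scale, k = 1 | 2.6–57.4% |
| Identity scale, binomial | 9.9–50.1% |
| Wilson | 14.5–51.9% |
| Clopper-Pearson | 11.9–54.3% |

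**5. Impossible limits.** The upper limit stays below 100% at 6/20. On a log scale it passes 100% from 12/20 (k = 0, 105.7%) or 10/20 (k = 1, 106.8%); on an identity scale, from 13/20 or 12/20.

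**6. Coverage of the full SAP model.** I simulated 1,500 trials at a 30% rate with timepoint, background therapy and baseline in the model. Assumptions: log link, change SD 4.5, within-subject correlation 0.6, baseline CAT N(20, 6) limited to 10–38, 10 subjects per background therapy. Fourteen trials without a finite interval were excluded.

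| Interval | Coverage | Median width |
|---|---|---|
| SAP primary, k = 0 | 99.1% | 0.52 |
| SAP primary, k = 1 | 99.9% | 0.61 |
| Same model, subject-clustered robust SE | about 94% | 0.46 |
| Wilson | 97.1% | 0.37 |

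In a second simulation, with rates of 30% to 60% and correlations of 0 to 0.9, the model-based interval covered at least 99.1% throughout.

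**7. Effect on the verdict.** On a log scale the lower limit is above 0 with any responder, as for Wilson and exact limits. On the normal approximation, the k = 0 and binomial standard errors both need at least 4/20. With k = 1 on an identity scale, 5/20 is needed (4 − 1.96 √4.8 = −0.29; 5 − 1.96 √6.25 = 0.10), so only a result of exactly 4/20 would differ.

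**The case against.** The strongest reply is that little turns on this. The error is conservative, N = 20 meets the stated aim with either standard error, and Protocol 9.1 plans no formal tests. SAP 8.4.5.3 already prespecifies a robust standard error to guard against misspecification, and the observed number and percentage will be reported. The larger inflation figures need a k or a response rate that the plan does not state. Part of the gap between a log-scale count interval and Wilson comes from the log scale, not from the variance.

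Much of this stands. On the log scale the like-for-like widths at 6/20 are 0.53 (k = 0) and 0.43 (binomial), against 0.37 for Wilson. With covariates in the model, the excess over the robust version is 0.52/0.46, about 13%, at k = 0 and 0.61/0.46, about 33%, at k = 1. The most defensible single figure is therefore a standard error about 1.2 times too large, at k = 0 and 30%. Limits above 100% also depend on the link: a robust standard error with a log link passes 100% from 17/20 (102.2%).

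None of it removes the error. The robust analysis neither decides success nor supplies the primary interval, and no binomial CI is attached to the observed percentage. No k ≥ 0 makes the primary variance right.

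**Conclusion.** The concern holds, and the plan should be corrected. Both the primary model and the sample-size calculation give a yes/no outcome the variance of a count. The direction is certain for any k ≥ 0; only the size depends on the unstated dispersion and the true response rate, and the form of the limits on the unstated link. The planning error, 2.449 against 2.049, rests on no assumption. The success verdict is not expected to change, apart from the narrow 4/20 case above. What is misstated is the precision of the only primary endpoint, with nominal 95% intervals that cover about 99% or more.

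A separate mismatch needs reconciling. Protocol 9.3.2 says: "Within subject correlation in responder status will be modeled using an unstructured covariance matrix". The SAP primary model has a timepoint term but no subject term. This does not cause the widening: moving the true correlation from 0 to 0.6 shifts the median log-scale standard error only from 0.424 to 0.429 (k = 0). Restoring the correlation alone would not correct the standard error.

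**What to change.** - Make the primary result the Week 12 responder n/N with a Wilson or Clopper-Pearson 95% CI.
- If covariate adjustment is to stay primary, use a binomial GEE clustered on subject with robust standard errors. Report a standardised proportion and keep the limits within 0–100%, for example with a logit link. This also restores the within-subject correlation that Protocol 9.3.2 requires.
- Align Protocol 1.1, 9.3.2 and 9.3.3 and SAP 8.4.5.2 and 8.4.5.3, including the Week 6 responder analysis.
- In Protocol 1.1 and 9.2 and SAP 5, replace the standard error of √6 with 2.049, and the SAP 5 interval with (1.98, 10.02) or the Wilson (14.5–51.9%) or exact (11.9–54.3%) interval for 6/20.
- Record the change in SAP 2.2.

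The cost is wording in both documents and simpler code, with no new data, visits or subjects.
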